9.4 Data Safety Monitoring Plan

Investigator/Sub-investigators, regulatory, CRS management, clinical research coordinators, clinical research associates, data managers, and clinic staff meet regularly in disease center Data Safety Monitoring Boards (DSMB) to review and discuss study data to include, but not limited to, the following:

- serious adverse events
- subject safety issues
- recruitment issues

- accrual
- protocol deviations
- unanticipated problems
- breaches of confidentiality

All toxicities encountered during the study will be evaluated on an ongoing basis according to the NCI Common Toxicity Criteria Version 4.0. All study treatment associated adverse events that are serious, at least possibly related and unexpected will be reported to the IRB. Any modifications necessary to ensure subject safety and decisions to continue or close the trial to accrual are also discussed during these meetings. If any literature becomes available which changes the risk/benefit ratio or suggests that conducting the trial is no longer ethical, the IRB will be notified in the form of an Unanticipated Problem submission and the study may be terminated.

All study data reviewed and discussed during these meetings will be kept confidential. Any breach in subject confidentiality will be reported to the IRB in the form of an Unanticipated Problem submission. The summaries of these meetings are forwarded to the UPMC Hillman Cancer Center Data Safety Monitoring Committee (DSMC) which also meets monthly following a designated format.

For all research protocols, there will be a commitment to comply with the IRB's policies for reporting unanticipated problems involving risk to subjects or others (including adverse events). DSMC progress reports, to include a summary of all serious adverse events and modifications, and approval will be submitted to the IRB at the time of renewal.

Protocols with subjects in long-term (survival) follow-up or protocols in data analysis only, will be reviewed bi-annually.

Both the UPMC Hillman Cancer Center DSMC as well as the individual disease center DSMB have the authority to suspend accrual or further investigate treatment on any trial based on information discussed at these meetings.

All records related to this research study will be stored in a locked environment. Only the researchers affiliated with the research study and their staff will have access to the research records.

Safety Monitoring

Adverse events are graded per CTCAE version 4. The primary endpoint for evaluating safety is dose-limiting toxicity (DLT). The period of observation for a DLT is from day -3 (first dose of nivolumab) through to 4 weeks after the completion of radiotherapy. A DLT is defined as:

1. Any \geq grade 3 adverse event that is related to nivolumab that does not resolve to grade 1 or less within 28 days;
2. A delay in radiotherapy of $>$ 2 weeks due to toxicity related to nivolumab;
3. Inability to complete radiotherapy due to toxicity related to nivolumab;

Patient safety will be monitored continuously using Bayesian methods. The presence or absence of a treatment-related DLT as defined above will be tabulated and used to compute the posterior probability of an excessive DLT rate. A 25% DLT is expected and acceptable; a 40% DLT rate is considered excessive. If the posterior probability is .80 or greater, that 40% or more of treated subjects experience a treatment related DLT, the study will be suspended pending review by the DSMC. This posterior probability will be calculated from the study's accumulating data and a weakly informative prior

distribution. If π denotes a random variable representing the proportion of subjects who will experience a treatment related DLT, we assume π has a prior beta distribution with parameters $a = .75$ and $b = 2.25$, which is consistent with an expected DLT rate of 25%.

Selected values of the posterior distribution $PP(\pi \geq .40 | \text{DLTs and prior})$ are shown in the table below. Also shown are the binomial probabilities of suspending the study for the observed count of DLT's.

Number of subjects observed to have treatment-related DLTs needed to suspend the study

Subjects	Treatment-Related DLTs	$PP(\pi > 25\%)^*$	$Pr(X \geq r p = 0.25)$
5	4	.937	.087
10	6	.805	.166
20	11	.857	.128
30	15	.812	.175
40	20	.861	.130
50	24	.836	.156
60	28	.815	.178
70	33	.858	.136
80	37	.842	.152
90	41	.828	.166
100	45	.816	.179
110	49	.805	.190
120	54	.843	.153
130	58	.834	.162

* π is the DLT rate. The minimum acceptable upper bound of a treatment-related DLT is 25%. $PP(\pi > 25\%)$ is the posterior probability that the RLT rate exceeds this 25% upper bound. This posterior probability of an DLT is calculated from the prior distribution, the number of subjects treated and the observed number of treatment-related RLTs. The table above presents the minimum number of subjects experiencing treatment-related DLTs (i.e., those DLTs judged to be possibly, probably, or related to Nivolumab) that would dictate suspension of the trial in accordance with the stopping rule.

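### The DLT suspension table carries the wrong labels: both probability columns are headed 25% but were computed at 40%, and the footnote contradicts the rule in the text

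*Combined protocol and SAP*

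**What the plan says.** Section 9.4 sets the two reference rates: "A 25% DLT is expected and acceptable; a 40% DLT rate is considered excessive". Its rule suspends the study, pending DSMC review, under this condition: "If the posterior probability is .80 or greater, that 40% or more of treated subjects experience a treatment related DLT". The prior is Beta(0.75, 2.25), with mean 0.25, and monitoring is described as continuous. The sentence introducing the table says that it shows posterior probabilities for a DLT rate of at least .40, and adds: "Also shown are the binomial probabilities of suspending the study for the observed count of DLT's".

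The table itself heads the posterior column as the probability that the rate exceeds 25%, and the binomial column as the tail probability at p = 0.25. The footnote names 25% as the upper bound and says that the tabulated posterior "is the posterior probability that the RLT rate exceeds this 25% upper bound". It then says that the listed counts are the ones that trigger suspension under the stopping rule.

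**The concern.** Two bounds are given for one safety rule: 40% in the text, 25% in the header and footnote. Because 25% is the rate the plan calls acceptable and 40% the rate it calls excessive, the labels decide how a DSMC reads the table. Under its heading, the last column is the chance of a false alarm at an acceptable rate. If it was computed at 40%, it is instead the chance of stopping when the rate is already excessive, which is close to the opposite meaning.

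The table lists only 14 sample sizes. With continuous monitoring, anyone evaluating the posterior between rows has to choose a bound, and the document supports both.

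**Working it through.** **Inputs, all from section 9.4.** Prior Beta(0.75, 2.25); cut-off 0.80; the 14 pairs of n (subjects) and r (DLTs) in the table, with their printed probabilities.

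**Formulas.**
- Posterior after r DLTs in n subjects: Beta(0.75 + r, 2.25 + n − r). Take its upper tail above 0.40 and above 0.25.
- Binomial column: Pr(X ≥ r) for X ~ Binomial(n, p), at p = 0.40 and p = 0.25.

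**One row by hand (n = 5, r = 4; printed .087).**
- p = 0.25: 5 × 0.25⁴ × 0.75 + 0.25⁵ = 0.01465 + 0.00098 = 0.0156.
- p = 0.40: 5 × 0.40⁴ × 0.60 + 0.40⁵ = 0.0768 + 0.0102 = 0.0870.

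The printed value is the p = 0.40 tail.

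**All rows.**

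| n | r | Posterior, printed | Posterior, >40% | Posterior, >25% | Binomial, printed | Binomial, p = .40 | Binomial, p = .25 |
|---|---|---|---|---|---|---|---|
| 5 | 4 | .937 | .8676 | .9793 | .087 | .0870 | .0156 |
| 10 | 6 | .805 | .8046 | .9795 | .166 | .1662 | .0197 |
| 20 | 11 | .857 | .8566 | .9960 | .128 | .1275 | .0039 |
| 30 | 15 | .812 | .8123 | .9973 | .175 | .1754 | .0028 |
| 40 | 20 | .861 | .8611 | .9994 | .130 | .1298 | .0006 |
| 50 | 24 | .836 | .8357 | .9996 | .156 | .1562 | .0004 |
| 60 | 28 | .815 | .8149 | .9998 | .178 | .1779 | .0002 |
| 70 | 33 | .858 | .8576 | >.999 | .136 | .1364 | .00005 |
| 80 | 37 | .842 | .8421 | >.999 | .152 | .1523 | <.0001 |
| 90 | 41 | .828 | .8284 | >.999 | .166 | .1663 | <.0001 |
| 100 | 45 | .816 | .8161 | >.999 | .179 | .1789 | <.0001 |
| 110 | 49 | .805 | .8051 | >.999 | .190 | .1902 | <.0001 |
| 120 | 54 | .843 | .8431 | >.999 | .153 | .1528 | <.0001 |
| 130 | 58 | .834 | .8336 | >.999 | .162 | .1623 | <.0001 |

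- Binomial column: 14 of 14 values match p = 0.40 to rounding. None comes within 0.02 of the p = 0.25 value. Shifting the count to r − 1 at p = 0.25 does not fit either.
- Posterior column: 13 of 14 match the 40% bound and none matches the 25% bound. The exception is n = 5: .937 is the tail of Beta(4.75, 2.25), which is 4 DLTs in 4 subjects. For 4 in 5 the posterior is Beta(4.75, 3.25), with tail .868.
- Counts: each printed r is the smallest count at which the posterior for a rate of at least 40% reaches 0.80.

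**What the footnote's bound would imply.** Keeping the 0.80 cut-off but using 25%, the smallest counts for n = 5, 10, 20, 30, 40, 100 and 130 are 3, 4, 7, 10, 13, 29 and 37. The printed counts are 4, 6, 11, 15, 20, 45 and 58.

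**Cumulative probability of suspension** (exact recursion over successive subjects).

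| Rule and looks | True rate 25% | True rate 40% |
|---|---|---|
| 40% bound, 14 tabulated looks | 3.2% | 45% |
| 40% bound, after every subject from the 5th to the 135th | 4.2% | 53% |
| 25% bound, 14 tabulated looks | 51% | >99% |

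**The case against.** The strongest reply is that the operative rule is not really in doubt. The text states it once with a cut-off, the sentence introducing the table names the same 40% bound, and all 14 counts obey it. The footnote gives no cut-off or counts of its own and refers back to the stopping rule. A DSMC that simply compares observed DLTs with the printed counts at the tabulated sample sizes would act as the text intends. The n = 5 error leaves that row's threshold at 4, because .868 still exceeds .80. Crossing a boundary leads to DSMC review, and the DSMC and the disease-centre DSMB can both suspend accrual without it. A cumulative suspension probability near one half at a true 40% rate is also unsurprising, since 40% is the rule's own boundary: over the tabulated looks it is 78% at a true 45% and 96% at a true 50%.

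All of this stands, and it limits the fault to the headers, the footnote and one value; the counts are sound for the 40% rule. It does not rescue the binomial column, which is the only operating characteristic printed for the rule and is attached to the wrong true rate. Nor does it help anyone who has to compute the posterior between rows. The lower set of counts is conditional: it arises only if a reader combines the footnote's 25% with the text's 0.80.

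**Conclusion.** The concern holds, and the table has to be corrected. Both probability columns are headed 25% but hold values for 40%, the footnote contradicts the text, and one of 14 posterior values is wrong (.937 for .868). As labelled, the table puts the per-look chance of suspending at an acceptable 25% rate at .087 to .190. The true values are .016, .020, .004 and .003 at n = 5, 10, 20 and 30, and below .001 from n = 40. So the rule looks much more prone to false alarms than it is, and its modest per-look chance of stopping at 40% goes unrecognised.

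The result rests only on the plan's own prior, cut-off and counts. The cumulative figures also assume independent DLTs at a constant rate, with each subject's outcome known at the look. Nothing here settles which bound is clinically appropriate.

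**What to change.** In section 9.4, make the text, column header and footnote state one and the same bound; the sponsor has to confirm which is intended. If it is the bound in the text, the counts stay as they are. The posterior column should then be headed as the probability of a rate of at least 40% and the binomial column as the tail at p = 0.40, the footnote reworded to match, and the n = 5 posterior changed to .868. If it is the footnote's bound, the counts and both columns must be recomputed.

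In either case, print the binomial tails at both 25% and 40% under correct headings. Cumulative suspension probabilities at the two rates are a useful addition, because monitoring is continuous and the tabulated tails are for single looks; they would let the DSMC confirm the 0.80 cut-off on the right figures.

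The cost is one corrected table and footnote in an amendment, with no new data or patients. The corrected table will openly show a per-look chance of only 9–19% of suspending at a true 40% rate.

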9.5 Gender and Ethnicity

The total accrual goal will be 135 patients without regard to all ethnic groups

9.6 Observer-Assessed Outcomes

Performance Status (PS): Performance status will be assessed using the ECOG performance status scale and must be 0-1 at baseline for study eligibility. Changes in ECOG PS will be tracked at all PRO endpoints.

Weight Loss: The degree of weight loss may contribute to fatigue, weakness and deconditioning. Weight loss during therapy will be documented as well as post-treatment weight changes.

Tracheostomy and Enteral Feeding Tube Status: The presence of either assistive device will be tracked prospectively at all PRO time points.

Charlson Comorbidity Index: Comorbidity will be documented by chart abstraction at baseline.

Head and Neck Cancer Specific Performance Status: The Performance Status Scale (PSS-HN)⁶⁸ is a clinician-rated instrument consisting of 3 questions: normalcy of diet, public eating, and understandability of speech. The PSS-HN has been psychometrically validated and recommended by the National Comprehensive Cancer Network for measurement of swallowing and speech

performance in patients with head and neck cancer. It is not a PRO; it can be completed quickly by the trialist without adding to patient burden.

Swallowing Endpoint: Swallowing outcomes will be measured as a secondary endpoint of this trial using modified barium swallow (MBS) studies according to the assessment schedule. A standardized contrast medium (Varibar® thin liquid and pudding contrast, Bracco Diagnostics, Inc. Princeton, NJ) and digitally record MBS studies (30 frames/second) must be used. Three swallowing outcomes will be rated by the SLP conducting the MBS study and reported by research staff: 1) laryngeal penetration (yes, no); 2) aspiration (no, sensate, silent), and 3) pharyngeal residue (no, < 50%, > 50%). These have been selected as universal items generally reported by swallowing clinicians that have been shown to significantly predict pneumonia in patients with oropharyngeal cancers. Prevalence of these dysphagia endpoints will be estimated at each time point.

9.7 Patient Reported Outcomes (PRO)

Quality of Life: Quality of life will be assessed using the Functional Assessment of Cancer Therapy – Head and Neck Cancer (FACT-H&N). The FACT-H&N (version 4)¹⁷ consists of a cancer-specific questionnaire, FACT-G, in addition to 12 H&N cancer-specific items (the HN subscale). FACT-G is a 27-item measure that assesses general cancer quality of life [Cella, 1993; Cella, 1997]. The FACT-G contains 4 subscales: physical, social/family, emotional, and functional well-being. Individuals are asked to indicate how true 27 statements are for them, using the past 7 days as the timeframe. Responses range from not at all (0), to very much (4) on a 5-point scale. Psychometric properties of the FACT-G have been examined in a variety of oncology populations with alpha coefficients ranging from .65 to .89 [Cella, 1997]. After reverse coding selected items in the physical and emotional subscales, items are summed to provide total subscale scores, which will be used in our analyses. Using this scoring, higher values reflect better quality of life.⁴⁵ The full FACT-H&N provides a summary score for overall head and neck cancer related QOL and has been used frequently in clinical trials.

Head and Neck Symptom Burden: The MD Anderson Symptom Inventory-Head & Neck (MDASI-HN¹²) measures treatment related symptom burden in head and neck cancer patients. The MDASI measures both severity and burden of symptoms and their effect on patients' daily activities, using a numeric rating scale of 0-10. This instrument includes 13 core symptoms and 9 head and neck specific items. The instrument was validated in a cohort of more than 200 patients. The coefficient alpha was highly reliable. The MDASI takes less than 5 minutes for patients to complete.^{12,13,69,70}

Swallowing and Voice: Data regarding swallowing perception and performance and voice outcomes will be obtained from the MD Anderson Dysphagia Inventory (MDADI)⁷¹ and Voice Handicap Index-10 (VHI-10).

The MDADI measures swallowing-related quality of life (QOL) in patients with swallowing dysfunction in a 20 – item written questionnaire. It evaluates the patient's physical (P), emotional (E) and functional (F) perceptions of swallowing dysfunction. This instrument has been psychometrically validated in head and neck cancer patients.

The VHI-10²³ is a patient self-assessment instrument that quantifies patients' perception of their voice handicap. It evaluates patient's physical (P), emotional (E), and functional (F) perceptions of voice and has shown to be highly reliable for internal consistency and test-retest stability. The VHI-10 utilizes a 10-item questionnaire in which the patient circles the response that most accurately reflects his or her own experience on a linear scale (from "never" to "always").

Return to Work: Return to work will be tracked prospectively following treatment. While this data is patient reported, it does not generate a score requiring psychometric validation. It has been judged to have face validity and is brief and practical for use in a clinical trial.

Appendix I Patient Reported Outcomes (PROs)

EQ5D 5L Health Questionnaire

Functional Assessment of Cancer Therapy – Head and Neck Cancer (FACT-HN)

MD Anderson Symptom Inventory-Head & Neck (MDASI-HN)

MD Anderson Dysphagia Inventory (MDADI)

VHI-10

VHI-10.pdf

FACT-HN.pdf

MDADI.pdf

MDASI-HN.pdf

EQ5D 5L Health Questionnaire.pdf

Appendix II: Modified Barium Swallow Study Form

MBS

Modified Barium Swallow Study Form

Phase II Trial of Adjuvant De-Escalated Radiation + Concurrent and Adjuvant Nivolumab for Intermediate-High Risk P16+ Oropharynx Cancer

INSTRUCTIONS: To be filled out by the speech pathologist after the modified barium swallow study. **Dates are recorded as mm-dd-yyyy unless otherwise specified.**

MBS PROTOCOL:

All MBS studies must follow a standard protocol as outlined below.

Additional bolus presentations or swallowing strategies may be tested after completing bolus trials in the study protocol, at the discretion of the clinician conducting the MBS study.

Studies will be done in lateral and AP views with focus fixed on the soft palate superiorly, cricopharyngeus inferiorly, lips anteriorly, and cervical spine posteriorly.

Video-recordings will require time code imprints accurate to 0.01 seconds (30 frames/second).

Video-recordings between 15-30 frames/second will be accepted as long as the recording rate is clearly documented in advance. Video-recordings below 15 frames/second will not be accepted.

Studies must be recorded in AVI or MPEG format. All centers must use the Kay Digital Swallowing Workstation for the studies; or alternatively, can convert files to AVI or MPEG format. Centers must use Varibar products. Consistencies and quantities are listed below. Liquids must be administered first to avoid confounding the results from remaining residue in the pharynx after solid consistencies.

A dime must be taped to the subject's chin during the swallowing study. The circular shape of the dime minimizes the impact of head rotation and the known diameter of the dime allows for calibration of pixels per cm and thus calculation of distances and areas on the lateral view of the x-ray.

Lateral view:

- 5mL thin (2 trials, tsp). Instruction to the patient: *please hold this in your mouth until asked to swallow.*
- 20mL thin (1 trial). Instruction to the patient: *please try to take the whole amount and hold it in your mouth until I ask you to swallow.* Self-administration is optimal, but clinician administration is acceptable.
- 5mL pudding (1 trial tsp). Instruction: *swallow when you are ready.*
- 1/2 cookie or cracker, barium coated - coated with 3 ml (1/2 tsp) of Varibar pudding (1 trial). Instruction to the patient: *chew this up and swallow when you feel comfortable and ready to swallow.*

A-P view:

10mL thin (1 trial). Instruction: slightly raise your chin (neutral position, not tucked or extended), hold this in your mouth until asked to

RATING RULES:

Rate MBS outcomes below on the basis of bolus trials in the University of Pittsburgh protocol. Do not rate based on additional bolus trials that are administered outside of the protocol or based on bolus trials in which a swallow strategy/posture was tested. Please select a SUMMARY RATING based on the highest level of impairment you observe on any bolus trial in the protocol.

MBS**Modified Barium Swallow Study Form****Phase II Trial of Adjuvant De-Escalated Radiation + Concurrent and Adjuvant Nivolumab for Intermediate-High Risk P16+ Oropharynx Cancer**

1 DATE OF MBS _____ - _____ - _____	2  TIME OF MBS 1. Baseline 2. After surgery (before adjuvant therapy) 3. Six months after treatment 4. Twenty-four months after treatment		
Outcome Variables	Definition	Scoring Rules (Rate the worst of impairment across all bolus trials in the MBS protocol)	Rating
3 LARYNGEAL PENETRATION	PENETRATION: Bolus enters the larynx but does not pass below the TVFs	Select "1" if LARYNGEAL PENETRATION occurred on any bolus in the protocol.	 No penetration (0)  Penetration (1)
4 ASPIRATION	ASPIRATION: Bolus enters the larynx and passes below the TVFs. SENSATE: attempts to eject aspirate from airway (e.g., cough, throat clear) SILENT: no effort to eject aspirate from airway (no cough, throat clear)	Select the highest level of aspiration that occurred during the protocol. Select "1" if SENSATE ASPIRATION occurred on any bolus in the protocol, but silent aspiration NEVER occurred. Select "2" if SILENT ASPIRATION occurred on any bolus in the protocol.	 No aspiration (0)  Yes, sensate (1)  Yes, silent (2)
5 PHARYNGEAL RESIDUE	RESIDUE: bolus remaining on or within the pharynx at the conclusion of the initial swallow. The conclusion of the initial swallow is when the hyoid bone returns to rest. If the patient spontaneously swallows several times to clear the bolus, residue is rated after the 1 st swallow attempt.	Rate the highest level of residue that occurred during the protocol. Select "0" is no residue or only pharyngeal coating occurred during the protocol. Select "1" if pharyngeal residue of <50% of the original bolus remained in the pharynx on any bolus in the protocol. Select "2" if pharyngeal residue of half or more of the original bolus	 No residue (0)  <50% pharyngeal residue (1)  ≥ 50% pharyngeal residue (2)

MBS**Modified Barium Swallow Study Form****Phase II Trial of Adjuvant De-Escalated Radiation + Concurrent and Adjuvant Nivolumab for Intermediate-High Risk P16+ Oropharynx Cancer**

		remained in the pharynx on any bolus in the protocol.	
--	--	---	--

PERSON COMPLETING FORM:

NOTE: This form is for reference only. The MBS information for each registered patient will be entered directly into the UPMC database.

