9.3 Secondary Objectives

Secondary endpoints include toxicity, recurrence patterns, overall survival, swallowing function, and patient-reported outcomes.

Toxicity. For each arm, all treated patients will be evaluated by CTCAE version 4.0. Descriptive statistics will be provided by grade and type of toxicity.). The proportion of radiation-attributable grade III/IV toxicities will be estimated with 95% confidence intervals. These confidence intervals will be informally compared to published rates for standard of care radiation. In addition, frequencies of toxicity by grade in each arm will be compared with the Jonckheere-Terstra test

Recurrence Patterns Kaplan-Meier estimates with confidence intervals will be prepared for local, regional and distant recurrence. In addition, cumulative incidence functions will be estimated for local, regional and distant recurrence as well as death in the absence of disease progression. Gray's test will be applied to test differences in cumulative incidence patterns between treatment arms.

Overall Survival. Overall survival will be determined as the time from registration onto the study until death from any cause. Patients who were alive at the time of analysis will be censored at the date last known alive. Kaplan-Meier estimates will be calculated, along with their corresponding 95% confidence intervals. The median, 1-year, and 2-year survival rates will be estimated. Only eligible and treated patients will be analyzed for overall survival (by arm).

Swallowing Function and Voice. Descriptive statistics will be provided with confidence intervals for swallowing function, evaluated using the MBS ratings, PSS-HN normalcy of diet scale, and the validated survey MDADI instrument. Longitudinal analysis will be performed on each of these measures. All eligible and treated patients (on both steps) will be analyzed for PSS-HN diet scale, MDADI, and VHI-10. The MBS analysis will be performed on eligible and treated patients only if accrued at vetted participating centers.

Quality of Life. The primary variable of interest in the QOL analysis is the individual change in the FACT-H&N total score from baseline (prior to TOS) to 6 months post-RT. The within-patient change in FACT_H&N score will be calculated and tested with the signed rank test or Friedman's test for more than 2 sequential observations per patient.

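### The stand-alone penetration item on the MBS form scores an aspiration-only patient the same as a normal swallower, so its prevalence can fall as patients worsen

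*Combined protocol and SAP*

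**What the plan says.** Appendix II asks the speech pathologist to rate two airway items over the protocol boluses.

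- **Item 3, penetration (0 or 1).** The definition begins "PENETRATION: Bolus enters the larynx but does" and goes on to require that the bolus stay above the true vocal folds. The item scores 1 "if LARYNGEAL PENETRATION occurred on any bolus in the protocol" and 0 otherwise. There is no third box for a patient who aspirated.
- **Item 4, aspiration (0, 1 or 2).** The definition begins "ASPIRATION: Bolus enters the larynx and passes" and continues to below the folds. The rule is "Select the highest level of aspiration that occurred during the protocol", with 1 for sensate and 2 for silent.
- **General rating rule.** "Please select a SUMMARY RATING based on the highest level of impairment you observe on any bolus trial in the protocol". The form does not say how this applies to item 3 when a bolus is aspirated.

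Section 9.6 lists penetration, aspiration and pharyngeal residue as three separate swallowing outcomes, chosen for their link to pneumonia, and states: "Prevalence of these dysphagia endpoints will be estimated at each time point". Section 9.3 names the MBS ratings among the swallowing measures and adds: "Longitudinal analysis will be performed on each of these measures". Neither section sets an order between items 3 and 4 or combines them.

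**The concern.** For a single bolus the two definitions exclude each other: the bolus either stays above the folds or passes below them. Aspiration is the more serious event, yet it does not count towards item 3. A 0 on item 3 therefore mixes two very different groups, those with no airway entry and those whose every airway entry went all the way through.

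This matters because penetration is to be reported as a separate series. A reader who sees penetration fall between baseline and 24 months will take it as recovery. Part of such a fall could instead be patients moving from penetration to aspiration. Section 1.8 calls MBS the trial's main objective functional measure, and Section 9 gives fewer adverse effects as part of the trial's purpose, so a misleading swallowing series would bear on a claim the investigators want to make.

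**Working it through.** The plan gives no figure to reproduce here. The check is of the scoring logic.

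**Step 1. Inputs.** Appendix II specifies six boluses: 5 mL thin twice, 20 mL thin once, 5 mL pudding once and a coated cookie once in lateral view, and 10 mL thin once in A-P view. On the form's definitions each bolus has one of four results: no entry, penetration, sensate aspiration, silent aspiration.

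**Step 2. Enumeration.** There are 4^6 = 4096 possible patterns. Applying the two scoring rules literally gives:

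| Item 3 | Item 4 | Meaning | Patterns |
|---|---|---|---|
| 0 | 0 | no airway entry | 1 |
| 1 | 0 | penetration only | 63 |
| 0 | 1 | aspiration only, sensate | 63 |
| 1 | 1 | penetration and sensate aspiration | 602 |
| 0 | 2 | aspiration only, at least one silent | 665 |
| 1 | 2 | penetration and silent aspiration | 2702 |

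The counts sum to 4096. They show which pairs can occur; they are not probabilities. The rows (0,1) and (0,2) are the problem: item 3 is 0 in patients who aspirate. The table also shows that one penetrating bolus is enough to hold item 3 at 1, whatever the other five do.

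**Step 3. Direction of change.** A patient who goes from penetration only to aspiration only moves from (1,0) to (0,1) or (0,2). Item 3 falls by 1 and item 4 rises by 1 or 2.

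**Step 4. Illustration (assumed numbers, not from the documents).** Of 100 assessed patients, 20 are penetration-only at baseline and m of them become aspiration-only.

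| m | Penetration (item 3) | Aspiration (item 4 at least 1) | Any airway entry |
|---|---|---|---|
| 0 | 20% | 0% | 20% |
| 5 | 15% | 5% | 20% |
| 10 | 10% | 10% | 20% |
| 20 | 0% | 20% | 20% |

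Nobody improves in any row, yet the first series falls.

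**Step 5. Can the size be found?** The gap between item 3 prevalence and the prevalence of any airway entry is A × s, where A is the aspiration rate and s is the share of aspirators with no penetration-only bolus among the six. Section 1.5 cites aspiration rates of 6% to 31% at one year or later in other IMRT cohorts. The documents give no value for s. Over its full range of 0 to 1, the gap is 0 to 6 points at A = 6% and 0 to 31 points at A = 31%. These are bounds, not an estimate.

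**Step 6. Does an ordered score repair it?** Define the score as item 4 + 1 if item 4 is at least 1, and otherwise as item 3. Then (0,0) gives 0, (1,0) gives 1, (0,1) and (1,1) give 2, and (0,2) and (1,2) give 3. Item 3 is used only where item 4 is 0, that is, where no bolus was aspirated. The score is therefore the same whether or not a rater counts an aspirated bolus as penetration.

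**The case against.** The strongest reply is that no information is lost. Item 4 sits on the same form, moves up when item 3 moves down, and is reported as its own outcome with sensate and silent aspiration kept apart. No total lets one offset the other. A reader might infer that the trial as a whole would count worsening as improvement, or that comparison over time is impossible. The documents do not support either reading. The false improvement exists on item 3 alone and disappears once items 3 and 4 are read together.

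Several further points stand.

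- The plan never says that item 3 should measure any airway entry. Prevalence of penetration as the form defines it is not biased; it answers a narrower question.
- The effect needs an aspirator with no penetration on any other bolus, and the documents do not say how common that is.
- Raters may not score literally. The general rule on worst impairment could lead some to mark 1 for an aspirator. The form is also marked as a reference copy, with data entered directly into a database whose entry rules are not shown.
- Section 9.3 speaks of the MBS ratings as a group and does not name penetration as a longitudinal endpoint by itself.
- MBS is optional under Section 4.3, secondary under Section 9.6, and analysed only at vetted centres under Section 9.3.

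These points limit the reach of the problem but do not remove it. Section 9.6 still commits to a separate penetration prevalence at each time point, and no rule links that item to aspiration. If raters do differ in how they score an aspirated bolus, that is a further reason not to analyse item 3 alone.

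**Conclusion.** The point holds in a limited form. On the form's wording, a patient whose only airway entries are aspirations scores 0 for penetration, so the separately reported penetration series is not monotone in severity and can fall as patients progress to aspiration. This rests on literal scoring of item 3.

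The size cannot be determined from the documents. A reader might want to attach a number of percentage points, but any such number depends on the unknown share s, and the aspiration rates cited come from other cohorts. Neither primary endpoint, the sample size nor the safety stopping rule is touched. It is a modest defect in a secondary, optional outcome, worth correcting because the correction costs so little.

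**What to change.** In Sections 9.3 and 9.6, replace the stand-alone penetration analysis with one ordered airway score derived from items 3 and 4:

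- 0: no airway entry
- 1: penetration only
- 2: sensate aspiration
- 3: silent aspiration

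The score equals item 4 + 1 if item 4 is at least 1, and item 3 otherwise. At each time point, report the prevalence of any airway entry (score 1 or more) and of any aspiration (score 2 or more). Use the ordered score in the longitudinal analysis. Pharyngeal residue stays as planned.

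Leave the wording of item 3 as it is. The derived score does not need a new definition, and changing it during the trial would mix two definitions across completed and future forms.

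The cost is a few lines of analysis text. The score uses ratings already collected, needs no new data, and can be computed for forms already completed.
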